## **ABBREVIATIONS**

CHW: Community Health Worker  
CSPS: Centre de Santé et de Promotion Sociale  
DSMC: Data and Safety Monitoring Committee  
HAZ: height-for-age z-score  
IRB: Institutional Review Board  
MUAC: mid-upper arm circumference  
RDT: rapid diagnostic test  
RUTF: ready-to-use therapeutic food  
SAM: severe acute malnutrition  
SD: standard deviation  
SES: socio-economic status  
UCSF: University of California San Francisco  
WAZ: weight-for-age z-score  
WHO: World Health Organization  
WHZ: weight-for-height z-score

## 1. INTRODUCTION

### 1.1 Background and Rationale

**Severe acute malnutrition (SAM) affects nearly 19 million children under the age of 5 annually.** Current World Health Organization (WHO) guidelines for treatment of SAM include outpatient treatment with ready-to-use therapeutic food (RUTF). Children with SAM often bear a large burden of infectious disease, have 9 times the risk of all-cause mortality compared to their well-nourished peers, and face a stronger risk of infectious mortality. Because malnutrition can suppress the immune system, children with SAM and co-existing infection are often asymptomatic. As a result, the WHO has recommended that the routine treatment of children with SAM include a broad-spectrum antibiotic. However, the evidence base for this recommendation is minimal. Two studies of amoxicillin as adjunctive therapy for SAM found mixed results. In Malawi, routine amoxicillin led to increased nutritional recovery and decreased mortality. In Niger, there was no effect of routine amoxicillin on either nutritional recovery or mortality. Importantly, a majority of the children included in the Malawi study had kwashiorkor, whereas children with kwashiorkor were excluded in Niger. A pooled analysis of the two studies found no benefit of amoxicillin for recovery. A third study of daily co-trimoxazole for complicated SAM additionally found no benefit for nutritional recovery or mortality. The role of antibiotics for mortality and nutritional recovery among children with uncomplicated severe acute malnutrition remains unclear.

**A recent cluster-randomized trial demonstrated that mass azithromycin distribution reduces all-cause mortality at the community level.** In Niger, Tanzania, and Malawi, mortality was reduced by nearly 14% in communities randomized to biannual mass single-dose azithromycin distribution to children 1-59 months in the MORDOR trial (*Macrolides Oraux pour Réduire les Décès avec un Oeil sur la Résistance*). The largest effects were seen in Niger, with nearly 1 in 5 deaths averted, and in children less than 6 months of age, with approximately 25% reduction in mortality.

**Azithromycin as adjunctive therapy may offer several advantages over amoxicillin or co-trimoxazole.** First, a single dose of azithromycin has a long half-life, and thus dosing could occur during outpatient follow-up visits and would not rely on caregiver dosing. Second, amoxicillin and co-trimoxazole are much more commonly used for routine treatment in many regions of sub-Saharan Africa than macrolides, and baseline resistance to these antibiotic classes tend to be much higher. Adjunctive therapy with azithromycin may be preferable, given overall reduced exposure compared to other classes. Third, evidence from the MORDOR study in Niger indicated a substantial reduction in mortality with the use of a single dose of azithromycin in children without established infection. Given that children with uncomplicated SAM by definition do not have an established infection, the rationale for antibiotic use may be similar for that among children in the general population who are receiving presumptive treatment. As children with malnutrition are at particularly high risk of mortality, this subgroup of the population may stand to see greater benefits from a similar antibiotic regimen that has been shown to be efficacious in the general population.

## 1.2 Design Overview

We propose a randomized controlled trial to examine the effect of the adjunctive administration of azithromycin compared to amoxicillin in the treatment of children aged 6-59 months with uncomplicated SAM. We will randomize children presenting to nutritional programs in Burkina Faso to a single dose of oral azithromycin or a short course of oral amoxicillin upon admission into the program and follow them at each weekly clinic follow-up visit up to 8 weeks following admission. All enrolled children will receive non-antibiotic routine care for uncomplicated SAM in Burkina Faso, which includes RUTF. Anthropometric and vital status data will be collected during follow-up. Weight gain and nutritional recovery over the 8-week study period will be compared by arm.

## 1.3 Objectives

**SPECIFIC AIM 1: Determine the effect of azithromycin on weight gain among children with uncomplicated SAM.** *We hypothesize that children randomized to receive azithromycin will experience greater weight gain over an 8-week period compared to those receiving amoxicillin.*

**SPECIFIC AIM 2: Determine the effect of azithromycin on nutritional recovery in children with uncomplicated SAM.** *We hypothesize that children randomized to receive azithromycin will have increased nutritional recovery 8 weeks after admission to the nutritional program compared to children receiving amoxicillin.*

## **2. STUDY DESIGN**

The proposed study is a pilot trial conducted in preparation for a future, larger trial. This randomized controlled trial is designed to determine the effect of administration of azithromycin compared to amoxicillin as part of the treatment of uncomplicated SAM in children aged 6-59 months on weight gain and nutritional recovery. We will randomize children presenting to nutritional programs at health centers in Burkina Faso to a single dose of oral azithromycin or a short course of oral amoxicillin upon admission into the program. Apart from the administration of antibiotics, all children will receive standard outpatient treatment for uncomplicated SAM as specified in the guidelines of the government of Burkina Faso, which includes therapeutic feeding with ready-to-use therapeutic food (RUTF). Enrolled children will be followed weekly at each routine clinic follow-up visit up until nutritional recovery. All enrolled children will return for a final study visit at 8 weeks following enrollment. Anthropometric and vital status data will be collected at each follow-up visit. Weight gain and nutritional recovery over the 8-week study period will be compared by arm.

### **2.1. Study Setting**

The trial will be conducted at Centre de Santé et de Promotion Sociale (CSPS) that run nutritional programs for children presenting with SAM. CSPSs are government-run integrated health centers linked to and overseen by district hospitals.

### **2.2. Recruitment and Eligibility Criteria**

#### **Recruitment**

Community health workers (CHWs) will be trained by the study team to actively seek cases of SAM in the study area and refer them to a study CSPS. CHWs will screen for SAM using tape to measure mid-upper arm circumference (MUAC) and will refer children with MUAC < 115 mm to a study CSPS.

Each participating enrollment site will be assigned at least one dedicated study team member who will enter data and conduct outcome assessments. The study team member will be either an existing member of enrollment site staff who will be trained for the study or an external study team member who will be placed at the site for the duration of the study.

This study team member will review the site logbook and/or medical records every day to identify children who are potentially eligible for participation, including both children referred by CHWs and children presenting independently. The team member will approach the parent or guardian of potentially eligible children to confirm eligibility according to the criteria listed below.

#### **Eligibility criteria for enrollment sites**

For inclusion in the pilot trial, sites must meet the following criteria:

1. More than 200 cases of severe acute malnutrition seen in 2017
2. Willing to participate in the trial
3. Participation approved by the district

#### **Eligibility criteria for individuals**

Eligible individuals are children aged 6-59 months with SAM who present to an eligible enrollment site during the study period and meet all of the following criteria:

*Inclusion criteria (all must be met):*

- Age 6-59 months
- Weight-for-height z-score (WHZ) < -3 SD or mid-upper arm circumference (MUAC) < 115 mm
- No nutritional edema
- Primary residence within catchment area of enrollment site
- Available for full 8-week study
- Has not been admitted to a nutritional program for the treatment of SAM in the 2 preceding weeks
- No antibiotic use in past 7 days
- No clinical complications requiring antibiotic treatment
- No clinical complications requiring inpatient treatment
- No congenital abnormality or chronic debilitating illness that would lead to predictable growth faltering or reduce likelihood of SAM treatment benefit (such as cerebral palsy, Down syndrome, congenital heart disease, cleft lip/palate, etc)
- No allergy to macrolides/azalides
- Sufficient appetite according to a feeding test with ready-to-use therapeutic food (RUTF)
- Appropriate written informed consent from at least one parent or guardian

*Exclusion criteria (any excludes):*

- Age < 6 months or > 59 months
- WHZ  $\geq$  -3 SD or MUAC  $\geq$  115 mm
- Primary residence outside catchment area of enrollment site
- Not available for full 8-week study
- Presence of nutritional edema
- Admission to a nutritional program for the treatment of SAM in the 2 preceding weeks
- Antibiotic use in past 7 days
- Clinical complications requiring antibiotic treatment
- Clinical complications requiring inpatient treatment
- Congenital abnormality or chronic debilitating illness that would lead to predictable growth faltering or reduce likelihood of SAM treatment benefit (such as cerebral palsy, Down syndrome, congenital heart disease, cleft lip/palate, etc)
- Allergy to macrolides/azalides
- Insufficient appetite according to a feeding test with ready-to-use therapeutic food (RUTF)
- Parent or guardian refuses to provide consent

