### **2.3. Randomization and Masking**

Children meeting inclusion criteria will be enrolled by local trained study personnel. At enrollment, children will be assigned a study identification number using the next unassigned number on a list identification numbers assigned to the site. Enrolled children will then undergo a baseline assessment. The baseline assessment includes data collection on demographics and socioeconomic status, anthropometric assessments, and a malaria rapid diagnostic test (RDT; see Figure 1 and Section 3 for details). After completion of the baseline assessment,

children will be randomized to receive either a single dose of directly observed oral azithromycin or a 7-day course of oral amoxicillin.

The randomization sequence will be generated by the UCSF investigators using R (R Foundation for Statistical Programming, Vienna, Austria). Children will be randomized in a 1:1 fashion to a single dose of azithromycin or a short course of oral amoxicillin. The randomization sequence will be linked to the study identification numbers. Randomized study arm assignments will be placed in sealed, opaque envelopes labeled with study identification numbers. When a child has been enrolled and has completed the baseline assessments, a CSPS nurse trained for the study will open the envelope to determine the allocation, and will administer study medication indicated as described in Sections 2.4 and 4.

To keep the allocation concealed, only the study nurse administering treatment will have access to the envelopes with the randomization allocations. The study nurse will open the envelope and administer treatment in a private room without the outcome assessor present. For each enrolled child, the study nurse will record whether or not azithromycin was administered on a paper form kept in a locked cabinet not accessible by the outcome assessor.

Given the nature of the intervention, participants and study personnel administering treatment will not be masked to treatment assignment. Outcome assessors will be masked to treatment assignment; this will be accomplished by assigning one CSPS nurse to administer treatment and a separate masked study team member to perform outcome assessments, including anthropometry, malaria RDT, and vital status updates.

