### Secondary Outcomes

- **Nutritional recovery by 8 weeks (Specific Aim 2).** Nutritional recovery will be defined as a child having WHZ  $\geq -2$  on two consecutive visits and no acute complication or edema for the past 7 days OR MUAC of  $\geq 125$ mm on 2 consecutive visits and no acute complication or edema for the past 7 days. The criteria chosen to define the recovery will be the same one we used to admit the child into the program.

- **Time to recovery.** Time from enrollment to nutritional recovery (defined above) will be calculated in days by subtracting the date of enrollment from the date of nutritional recovery.
- **Nonresponse at 8 weeks.** Nonresponse will be documented if a child does not meet the criteria for nutritional recovery at 8 weeks.
- **Transfer to inpatient care.** The occurrence, date, and reason for transfer from outpatient to inpatient treatment will be recorded.
- **Mortality by 8 weeks.** Vital status will be assessed at all follow-up time points and mortality will be defined as death during the study period. Date of death will be recorded.
- **Clinical signs of infection.** At all follow-up time points, clinical signs of infection will be recorded, including care-giver reported experience of fever, diarrhea, vomiting, and respiratory infection/cough and clinical diagnoses made at by site personnel
- **Adverse events.** Adverse events will be reported at all follow-up time points (defined in Section 5).
- **HAZ.** Height or length will be measured at all follow-up time points and height-for-age z-scores will be calculated.
- **MUAC.** Mid-upper arm circumference will be measured at all follow-up time points.
- **WAZ.** Weight will be measured at all follow-up time points and weight-for-age z-scores will be calculated.
- **WHZ.** Weight and height, assessed at all follow-up time points, will be used to calculate weight-for-height z-scores.
- **Malaria.** Rapid diagnostic tests for malaria will be conducted at baseline and week 8 to determine malaria infection status.
- **Intestinal microbiome:** Rectal swabs will be collected in a random subset of children at baseline and at week 8.

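### The WHZ/MUAC exclusion criterion is not the negation of the inclusion criterion: it shuts out every child who meets only one of the two

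*Combined protocol and SAP*

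**What the plan says.** The individual eligibility criteria in Section 2.2 are two lists. Every item on the inclusion list must be met, and its anthropometric item is "Weight-for-height z-score (WHZ) < -3 SD or mid-upper arm circumference (MUAC) < 115 mm". Either sign satisfies that item.

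The second list is headed "Exclusion criteria (any excludes", so one item is enough to reject a child. Its anthropometric item is "WHZ $\geq$ -3 SD or MUAC $\geq$ 115 mm".

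Four other statements bear on which rule is meant:

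- Section 2.2, Recruitment: community health workers "will refer children with MUAC < 115 mm to a study CSPS", with no WHZ condition.
- Section 2.2, Recruitment: the study team member at the site approaches the parent or guardian "to confirm eligibility according to the criteria listed below". Both lists follow.
- Section 2.3: "Children meeting inclusion criteria will be enrolled by local trained study personnel". Only the inclusion list is named.
- Section 2.5, Secondary Outcomes: recovery has a WHZ route and a MUAC route, joined by OR ("no acute complication or edema for the past 7 days OR MUAC of" a stated threshold). It adds: "The criteria chosen to define the recovery will be the same one we used to admit the child into the program".

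The Revisions History records no change to the WHZ/MUAC pair.

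**The concern.** The exclusion item reads as an attempt to restate the inclusion item in the negative. Each inequality was reversed, but the connective stayed 'or'. The two items therefore cannot both be followed for a child who meets one sign and not the other.

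What is at stake is who is enrolled. A site that works through the exclusion list literally turns away every single-sign child, including children sent in by community health workers on MUAC who prove to have WHZ at or above -3. It recruits a both-signs population, narrower than the one described elsewhere in the protocol. A site that follows the inclusion list recruits an either-sign population, and each single-sign child it enrols meets a written exclusion criterion and could be recorded as an eligibility deviation. If sites differ, the population differs by site. Section 2 describes the study as a pilot for a larger trial, so uncorrected wording could carry forward.

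**Working it through.** No stated figure has to be reproduced here; the check is one of logic.

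**Inputs**, all from the eligibility lists in Section 2.2. Let A be WHZ < -3 SD and B be MUAC < 115 mm.

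- Inclusion: A or B.
- Exclusion as written: (not A) or (not B).
- True complement of the inclusion rule, by De Morgan's law: not (A or B) = (not A) and (not B).

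**All four combinations:**

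| WHZ | MUAC | Inclusion met | Excluded as written | Conflict | Excluded if 'and' |
|---|---|---|---|---|---|
| < -3 | < 115 mm | yes | no | no | no |
| < -3 | ≥ 115 mm | yes | yes | **yes** | no |
| ≥ -3 | < 115 mm | yes | yes | **yes** | no |
| ≥ -3 | ≥ 115 mm | no | yes | no | yes |

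**As written.** Inclusion admits 3 of 4 combinations and the exclusion item rejects 3 of 4. They overlap on 2 of the 3 admitted, which leaves 3 - 2 = 1 of 4 eligible: the child who meets both signs.

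**With 'and'.** The exclusion item rejects 1 of 4 and overlaps with none of the 3 admitted. All 3 stay eligible, with no gap and no overlap.

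**Two illustrative children.** MUAC 110 mm with WHZ -2.5 meets inclusion on MUAC and is excluded on WHZ. WHZ -3.5 with MUAC 118 mm meets inclusion on WHZ and is excluded on MUAC.

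**Which reading the rest of the text supports.** Referral on MUAC alone fits the either-sign rule. So does enrolment on the inclusion list. So does a recovery definition with two routes tied to the admission criterion: if every child had to meet both signs, that tie would not identify a route for anyone. Against this, the recruitment text sends site staff to both lists, and no sentence says that one list overrides the other.

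**The case against.** The strongest reply is that the intent is plain and the harm hypothetical. Section 2.3 enrols on the inclusion list, and the referral and recovery rules make sense only if one sign is enough. The protocol also has safeguards. Section 3.1 requires a 2-day training, a quiz score above 80%, investigator oversight in the first week of enrolment and monthly refreshers. Section 6.3 has data collection monitored weekly. Section 8 has enrolment progress reviewed after 1 month. A site that kept rejecting MUAC-only referrals would probably be noticed. The study forms in Appendix 2 are not in the text reviewed, so the wording staff actually use at screening cannot be checked. Finally, the exclusion list is loose elsewhere: the consent pair is not an exact negation either, because one parent could consent while another refuses.

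Much of this stands. The intent can be inferred, and whether any site would apply the item literally is not known. But acting on the inferred intent means disregarding an explicit exclusion criterion, and training and monitoring do not correct the text that staff are trained on. Loose wording in the consent pair neither causes nor removes the WHZ/MUAC conflict.

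**Conclusion.** The concern holds. The anthropometric exclusion item contradicts the inclusion item for 2 of the 3 combinations that inclusion admits, and the literal rule leaves 1 of 4 combinations eligible. The logic needs no assumption beyond the two list headings: all inclusion items required, any exclusion item sufficient.

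The limits are clear. The counts are of combinations, not children, and the share of children meeting only one sign cannot be computed from the protocol. Eligibility is settled before randomization, so the slip does not itself bias the arm comparison. The primary outcome definition and the analysis models in Section 9.2 are unchanged, and the power calculations in Section 9.1 do not use the eligibility rule. The effect is on the population enrolled and on consistency between sites. It should be fixed because the rule is operative and gives the wrong population if followed as written.

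A separate, smaller gap lies in Section 2.5. Tying recovery to the admission criterion does not say which route applies to a child who met both signs at admission. That gap exists under the inclusion 'or' as well, and the main finding does not depend on it.

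**What to change.** In the Section 2.2 exclusion list, change the connective so that the item reads WHZ ≥ -3 SD **and** MUAC ≥ 115 mm, or delete the item, since the inclusion list already covers it. If the sponsor did mean to require both signs, the inclusion item must change instead, and the referral and recovery text must be brought into line with it. Whichever is chosen, check that the screening form and training material carry the same rule.

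Separately, reconcile Sections 2.2 and 2.5 so that the recovery rule has a single reading for a child who met both signs at admission; which reading is for the sponsor to decide.

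The cost is one word or one deleted item, plus one clarifying sentence in Section 2.5. No extra children, visits or procedures are needed.

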### **2.3. Randomization and Masking**

Children meeting inclusion criteria will be enrolled by local trained study personnel. At enrollment, children will be assigned a study identification number using the next unassigned number on a list identification numbers assigned to the site. Enrolled children will then undergo a baseline assessment. The baseline assessment includes data collection on demographics and socioeconomic status, anthropometric assessments, and a malaria rapid diagnostic test (RDT; see Figure 1 and Section 3 for details). After completion of the baseline assessment,

children will be randomized to receive either a single dose of directly observed oral azithromycin or a 7-day course of oral amoxicillin.

The randomization sequence will be generated by the UCSF investigators using R (R Foundation for Statistical Programming, Vienna, Austria). Children will be randomized in a 1:1 fashion to a single dose of azithromycin or a short course of oral amoxicillin. The randomization sequence will be linked to the study identification numbers. Randomized study arm assignments will be placed in sealed, opaque envelopes labeled with study identification numbers. When a child has been enrolled and has completed the baseline assessments, a CSPS nurse trained for the study will open the envelope to determine the allocation, and will administer study medication indicated as described in Sections 2.4 and 4.

To keep the allocation concealed, only the study nurse administering treatment will have access to the envelopes with the randomization allocations. The study nurse will open the envelope and administer treatment in a private room without the outcome assessor present. For each enrolled child, the study nurse will record whether or not azithromycin was administered on a paper form kept in a locked cabinet not accessible by the outcome assessor.

Given the nature of the intervention, participants and study personnel administering treatment will not be masked to treatment assignment. Outcome assessors will be masked to treatment assignment; this will be accomplished by assigning one CSPS nurse to administer treatment and a separate masked study team member to perform outcome assessments, including anthropometry, malaria RDT, and vital status updates.

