## 2.7. Study Team, Roles, Responsibilities

- **Investigators (UCSF).** The UCSF investigators will be responsible for the overall study design and implementation, data management and monitoring, data analysis, and dissemination of results in collaboration with UCSF investigators. The UCSF investigators will design and implement trainings for study procedures and maintain weekly communication with local Burkina Faso study staff.
- **Investigators (CRSN).** The CRSN investigators will be responsible for overall study design, implementation, data management and monitoring, data analysis, and dissemination of results in collaboration with UCSF investigators. The Burkina Faso investigators will oversee all local study activities, including training and regular supervision and monitoring of local study staff.
- **Medical Monitor.** The Medical Monitor will provide clinical oversight for the enrolled children. Study Team Members will report serious adverse events to the Medical Monitor within 24 hours of occurrence, and the Medical Monitor will determine whether or not the event is likely to be related to the study drug. In addition, the Medical Monitor will provide clinical guidance for the adverse event as needed. The Medical Monitor will participate on the Data and Safety Monitoring Committee.
- **Data and Safety Monitoring Committee.** The Data and Safety Monitoring Committee will provide independent oversight of data quality and patient safety during the course of the trial. See Section 8 for details.
- **Study Team Members (CRSN).** Study Team Members at CRSN will be responsible for implementation of all study procedures as described in Section 3, including recruitment, consent, enrollment and randomization, drug administration, and collection of all study data, including anthropometric and malaria assessments.
  - **CSPS Nurse.** A nurse at each CSPS will be trained to determine the randomization allocation of enrolled children by opening the envelopes and to administer azithromycin if indicated.
  - **Outcome Assessor.** One outcome assessor for each site will be trained to manage consent, enrollment, and collection of all study data, including outcome assessments.

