##### **Study Medication Description**

Zithromax® for oral suspension is supplied in bottles containing azithromycin dehydrate powder equivalent to 1200mg per bottle and the following inactive ingredients: sucrose; tribasic anhydrous sodium phosphate; hydroxypropyl cellulose; xanthan gum; FD&C Red #40; and flavoring including spray dried artificial cherry, crème de vanilla, and banana. After constitution, a 5mL suspension contains 200mg of azithromycin.

The oral amoxicillin routinely used at each CSPA for treatment of uncomplicated severe acute malnutrition will be used for this trial.

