## 9. STATISTICAL METHODS

### 9.1. Sample Size and Power

**Specific Aim 1** We assume that inclusion of 300 children (150 randomized to each arm) will provide 80% power to detect a 27% increase in weight gain (g/kg/day) in children receiving azithromycin compared to children receiving amoxicillin at an alpha of 0.05. Assumptions for this calculation were based on the pattern of weight gain reported in a trial of routine amoxicillin for uncomplicated SAM in Niger comparing children receiving amoxicillin to placebo over time. We assumed an average weight gain of 4.9 g/kg/day in the amoxicillin arm, with a standard deviation of 3.9 g/kg/day, and loss to follow-up of 10%. A 27% increase corresponds to a mean difference in weight gain of 1.3 g/kg/day, or an average weight gain of 6.2 g/kg/day in the azithromycin arm.

This calculation was performed in Stata using the following command:

```
power twomeans 4.9, sd(3.9) alpha(0.05) power(0.8) n(270)
```

**Specific Aim 2.** Inclusion of 300 children (150 randomized to each arm) will provide 80% power to detect an 15 percentage point difference in the proportion of children achieving nutritional recovery in the azithromycin arm compared to the amoxicillin arm. Assumptions for this calculation were based on nutritional recovery reported in the amoxicillin arm of a trial of routine amoxicillin for uncomplicated SAM in Niger. We assumed that 66% of children in the oral amoxicillin arm would achieve nutritional recovery and a loss to follow-up of 10%.

This calculation was performed in Stata using the following command:

```
power twoproportions 0.66, alpha(0.05) power(0.8) n(270)
```

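### Allocation runs on site-specific ID lists, but no site stratification or blocking is stated and the Aim 1 and Aim 2 models have no site term, so precision is lost modestly and avoidably

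*Combined protocol and SAP*

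**What the plan says.** Section 2.3 describes allocation in three steps. Each enrolled child receives an ID "using the next unassigned number on a list identification numbers assigned to the site". On the sequence itself it says "The randomization sequence will be generated by the UCSF investigators using R", and gives the ratio: "Children will be randomized in a 1:1 fashion to a single dose of azithromycin or a short course of oral amoxicillin". Finally, "The randomization sequence will be linked to the study identification numbers", and the assignments go into sealed, opaque envelopes labelled with the IDs. Stratification, blocking, minimisation or any other restriction is not mentioned there or elsewhere in the document.

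The sample size in section 9.1 is framed as equal arms: "We assume that inclusion of 300 children (150 randomized to each arm) will provide 80% power".

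In section 9.2 the Aim 1 linear model has a treatment indicator and nothing else. The Aim 2 log-binomial model has the same single term. The secondary anthropometric models add the baseline value, but not site.

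Site also determines who collects the data. Section 2.7 says "One outcome assessor for each site will be trained to manage consent, enrollment, and collection of all study data", while section 2.2 is looser: "Each participating enrollment site will be assigned at least one dedicated study team member who will enter data and conduct outcome assessments".

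**The concern.** Linking the sequence to site-held ID lists means that allocation is issued site by site. Sites can differ in case mix, feeding support, attendance and measurement practice, and these can move both weight gain and recovery. A multi-site trial usually deals with this by restricting the sequence within site, by putting site in the model, or both. As written, this plan states neither.

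What is at stake is precision. Under an unrestricted sequence, site differences enter the arm comparison as random error that the stated models leave in the residual. The trial is described as a pilot for a larger one, so clean within-site comparisons would also help to plan its successor.

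**Working it through.** **1. Reproduce the plan's figures (section 9.1).** Inputs: amoxicillin mean 4.9 and SD 3.9 g/kg/day, alpha 0.05 (two-sided by the command's default), and 300 × 0.90 = 270 evaluable, or 135 per arm.
- SE of the difference = 3.9 × √(2/135) = 0.475 g/kg/day.
- Solving the two-sample t-test for 80% power gives a difference of 1.335 g/kg/day, and 1.335/4.9 = 27.2%. The plan says 27%.
- Aim 2, 66% against 81% with 135 per arm: power 80.1%. The plan says 80%.

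Both figures reproduce.

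**2. Unequal totals, if the sequence is unrestricted (assumption).** The size of one arm is Binomial(300, 0.5), with SD √(300 × 0.25) = 8.7.
- P(exactly 150:150) = 4.6%; P(140:160 or worse) = 27%; P(135:165 or worse) = 9.4%.
- The central 95% range for one arm is 133 to 167.
- At 133:167 the evaluable split is 119.7:150.3, so SE = 3.9 × √(1/119.7 + 1/150.3) = 0.478. Power is 79.5% for Aim 1 and 79.3% for Aim 2.

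The loss is under 1 point.

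**3. Imbalance within sites, under the same assumption.** The number of sites is not given, so equal sites are assumed. P(60:40 or worse at one site of size m) = 2 × P(X ≤ 0.4m), with X ~ Binomial(m, 0.5). For S sites, P(at least one) = 1 − (1 − p)^S.

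| Sites | Children per site | One given site | At least one site |
|---|---|---|---|
| 3 | 100 | 5.7% | 16% |
| 6 | 50 | 20% | 74% |
| 10 | 30 | 36% | 99% |

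**4. Value of site balance plus a site term.** Let ρ be the share of weight-gain variance explained by site (assumption). Balance and adjustment together multiply the variance of the arm difference by (1 − ρ). This equals 270/(1 − ρ) − 270 extra children. Without them, site contributes an error with SD of about 0.475 × √ρ.

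| ρ | Equivalent extra children | Power at 1.335 | Site error SD (g/kg/day) |
|---|---|---|---|
| 0 | 0 | 80.0% | 0 |
| 2% | 5.5 | 80.8% | 0.07 |
| 5% | 14.2 | 82.0% | 0.11 |
| 10% | 30.0 | 84.0% | 0.15 |

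**5. Separate the design part from the model part.** With a site term, the variance of the arm difference is proportional to 1/Σ(a × b/n), where a and b are a site's arm counts and n = a + b. Perfect balance gives Σ = 270/4 = 67.5. Simulating simple randomisation with 270 evaluable children, the variance relative to perfect balance averages 1.011, 1.023 and 1.039 for 3, 6 and 10 equal sites. Blocking itself is therefore worth about 3, 6 or 10 children (270 × 0.011, 0.023, 0.039). For 3 or 6 sites at ρ of 5% to 10%, most of the gain in step 4 comes from the model term.

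**6. Downside of the site term.** If the sequence was unrestricted and site explains nothing, adding the term raises the variance by about 0.8%, 1.9% or 3.5% for 3, 6 or 10 sites, compared with the arm-only model.

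**The case against.** The strongest reply is that silence does not mean an unrestricted sequence. The R code may already block by site, and the planned 150 per arm is compatible with that. This stands: the probabilities in steps 2 and 3 are conditional, and the document neither states nor excludes the design they assume. It does not answer the analysis half of the point, because section 9.2 does write out the models and they have no site term.

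Two stronger readings are tempting, and the documents support neither.
- A reader might infer that the trial is underpowered because 150 per arm is not guaranteed. Step 2 shows that the cost is negligible, and blocks within site do not guarantee exactly 150:150 either if a site's last block is incomplete.
- A reader might infer that each site is a single assessor with its own amoxicillin, so that imbalance biases the comparison. Section 2.2 allows more than one team member per site, and section 3.2 uses two people for anthropometry. Gold-standard agreement, monthly refresher training, triplicate measurement and twice-daily scale checks limit drift. The primary outcome is change within a child, so a constant scale offset largely cancels. On the drug, "The oral amoxicillin routinely used at each CSPA for treatment of uncomplicated severe acute malnutrition will be used for this trial" must be read with the procurement paragraph of section 4, where the study team buys it. Any product difference would affect only the amoxicillin arm, so site balance could not remove it.

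Simple randomisation is also unbiased, and its test is valid. Finally, blocks carry a risk when the nurse and caregivers know the treatment. That is a reason to choose block sizes with care. Section 2.7 gives consent and enrolment to the outcome assessor, who is masked and, under section 2.3, has no access to the envelopes or treatment forms. The protection depends on that masking holding within a small health centre.

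**Conclusion.** The point holds as a modest, avoidable loss of precision. The stated plan neither balances site nor accounts for it, although the ID lists already exist by site. With ρ of 2%, 5% or 10%, balance and a site term together are worth about 6, 14 or 30 of 270 evaluable children, or about 1, 2 or 4 points of power for Aim 1. These figures rest on an assumed site share of variance, equal evaluable arms of 135 and the plan's own SD. The split between blocking and modelling also depends on the unknown number of sites. The gain for Aim 2 was not quantified separately. Nothing here implies systematic bias, an invalid test or an inadequate sample size.

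**What to change.** In section 2.3, state how the sequence is generated: separately for each site's ID list, in random permuted blocks of varying size. The sizes should be known only to the person at UCSF who generates the list. Sizes such as 4 and 6 would serve. Blocks of 2 should be avoided, because anyone who knows the first allocation and infers the block boundary knows the second.

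In section 9.2, add site as a factor to the Aim 1 linear model and the Aim 2 recovery model. The modified Poisson fallback already in the plan covers non-convergence of the log-binomial model with the extra terms.

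If envelopes are already packed, leave the sequence alone, report the method actually used and add the site term before any unmasked analysis.

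The cost is a few lines of R and a sentence or two in each section. The downsides are a few degrees of freedom, slight predictability for the unmasked nurse, and the small variance penalty in step 6 if the sequence was unrestricted and site proves irrelevant.
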